7.1 Sample Size Determination

We approximated power and sample size using a simpler model comparing the two groups on change scores in behavioral effects (threat attention bias, reactive aggression) and brain activation (amygdala and striatal response to non-reward) from baseline to addback. With 15 subjects per group, we have 80% power to detect effect sizes of 1.10, which are large and consistent with our previous study (see Preliminary Data). We posit that if treatment with supra physiologic levels of reproductive hormones does not produce large enough differences in neural circuits between HS+ and HS- to be detected in a relatively small sample of women, then this line of research, which involves significant participant burden, is not worth pursuing. Moreover, given the experimental nature of the proposed research, our effect size estimates are more similar to those seen in experimental animal research than in traditional human clinical trials. Nonetheless, our own and other previous clinical research supports our hypothesized large effect. Studies comparing participants with major depression and controls have yielded effect sizes (Cohen's d) ranging from 1.15 to 2.05 in dorsomedial PFC responsivity to negative emotional stimuli (Grimm et al., 2008; Hooley et al., 2005; Moses-Kolko et al., 2010) and from 1.0 to 1.56 in ventral striatum reactivity to reward (Epstein et al., 2006; Moses-Kolko et al., 2011; Moria J Smoski et al., 2009). Studies examining the association between amygdala activation and depressive symptom severity have yielded effect sizes (Cohen's d) ranging from 1.62 to 2.76 (Hamilton & Gotlib, 2008; Moses-Kolko et al., 2010).

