Sensitivity Analysis. In addition to the statistical tests described below, we will use sensitivity analyses to evaluate the robustness of the study's main results to reasonable perturbations of the statistical methods and assumptions used and to help ensure reproducibility of the main results. Sensitivity analysis will address the inclusion/exclusion of questionable data values (i.e., outliers), the use of alternative methods of coping with missing values and dropouts, and modeling assumptions.

Hypothesis testing. We have detailed both the null and alternative hypotheses we will test below. For all hypothesis tests, we will use the Bonferroni method to correct for multiple comparisons. All hypothesis tests that are observed to be not statistically significant will be reported as being inconclusive. In accordance with the ICMJE and Consort Statement, all statistical estimates of population parameters will be tabulated along with confidence intervals. The interpretation of confidence intervals will be an integral part of the data analysis in concert with the statistical hypothesis tests.

Power calculations overview. We have based our power calculations on previous studies of similar effects (i.e, not pilot studies) with N greater than or equal to 30. Given that prior literature suggests large effect sizes for Aims 1 and 2, we believe that point-estimates will yield relatively accurate power calculations.

Aim 1: To determine the extent to which irritability is characterized by dysfunctional threat processing during reproductive hormone challenge relative to baseline in HS+ and HS-.

Null hypothesis 1: HS+ is not characterized by behavioral activation in the context of potential threat during periods of hormone change in the target population.

Alternative hypothesis 1: HS+ is characterized by behavioral activation in the context of potential threat during periods of hormone change in the target population. Given this hypothesis, we will test the following sub-hypotheses:

Null hypothesis 1a: HS+ is not characterized by threat attention bias during hormone addback relative to baseline in the target population.

Alternative hypothesis 1a: HS+ is characterized by threat attention during hormone addback relative to baseline in the target population.

Independent variables: Group (HS+ versus HS-) and Phase (Visit 3-baseline versus Visit 6-hormone addback)

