Dependent variable: Threat attention bias will be measured using the visual dot probe task at study visits 3 and 6. Threat attention bias will be calculated for the angry-neutral trials by subtracting the mean reaction time (measured in milliseconds) on trials where the asterisk

appears on the same side as the angry face from the mean reaction time on trials where the asterisk appears on the same side as the neutral face.

Analysis: 2x2 Repeated Measures ANOVA will be used to analyze the effects of Group (HS- vs. HS+) and Phase (baseline vs. hormone addback) on threat attention bias.

Power: We used G*Power 3.1 for Mac to calculate power. We anticipate an effect size $f=0.3$ based on a previous study of threat attention bias in those with and without mood dysregulation (Hommer et al., 2014). If we set $\alpha=.05$, we will have 87% power to reject the null hypothesis with a total sample size of $N=30$.

Null hypothesis 1b: HS+ is not characterized by reduced amygdala-medial PFC connectivity in response to threatening stimuli during hormone addback relative to baseline in the target population.

Alternative hypothesis 1b: HS+ is characterized by reduced amygdala-medial PFC connectivity in response to threatening stimuli during hormone addback relative to baseline in the target population.

Independent variables: Group (HS+ versus HS-) and Phase (Visit 3-baseline versus Visit 6-hormone addback)

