Dependent variable: Amygdala-medial PFC connectivity will be assessed during the implicit face emotion processing fMRI task at study visits 3 and 6. Functional connectivity expresses the statistical dependency among activations in different brain regions and results in undirected (symmetrical) connectivity matrices and will be calculated according to standard procedures (Walsh et al., 2017). We will use a generalized psychophysiological interaction (gPPI) approach for detecting context-dependent functional connectivity (Cisler et al., 2014; McLaren et al., 2012). Replicating the methods of Walsh et al. (2017), we will use an ROI approach to target the amygdala, which will be defined using the Harvard-Oxford subcortical atlas. Voxel-wise models will be used to evaluate connectivity with the amygdala seed. For each participant, mean fMRI time courses will be extracted from the amygdala seed using the “fslmeans” program in FSL, then multiplied by each psychological regressor of interest (i.e., task condition) to form the PPI interaction terms. The gPPI model will include physiological and psychological regressors, as well as their interaction terms to describe the unique effect of these interactions above and beyond the main effects of seed time courses and task conditions. Our primary contrast of interest will evaluate the difference between connectivity during presentation of threatening stimuli versus non-threatening stimuli. This allows for the characterization of connectivity patterns specific to threat processing.

Analysis: Group and phase differences will be evaluated with respect to seed-based connectivity specific to threat processing using a 2x2 mixed effects analysis with Bayesian estimation techniques with FMRIB Local Analysis of Mixed Effects (Smith et al., 2004).

Clusters will be thresholded at $Z>2.58$ or $p<.005$ corrected with a minimum contiguous cluster size of 8 (Walsh et al., 2017).

Power: We used G*Power 3.1 for Mac to calculate power. While few studies have examined changes in amygdala-PFC between those with and without depression following treatment, the few extant studies yielded large effects ($d=1.3$) (Straub et al., 2017). If we anticipate an effect size $f=.5$ and set $\alpha=.05$, we will have greater than 99% power to reject the null hypothesis with a total sample size of $N=30$.

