We approximated power and sample size using a simpler model comparing the two groups on change scores from baseline to addback. With 15 subjects per group, we have power to detect effect sizes of 1.10, which are large and consistent with our previous study. We posit that if treatment with supra physiologic levels of reproductive hormones does not produce large enough differences in neural circuits between HS+ and HS- to be detected in a relatively small sample of women, then this line of research, which involves significant participant burden, is not worth pursuing. Moreover, given the experimental nature of the proposed research, our effect size estimates are more similar to those seen in experimental animal research than in traditional human clinical trials. Nonetheless, our own and other previous clinical research supports our hypothesized large effect. Studies comparing participants with major depression and controls have yielded effect sizes (Cohen's d) ranging from 1.15 to 2.05 in dorsomedial PFC responsivity to negative emotional stimuli (Grimm et al., 2008; Hooley et al., 2005; Moses-Kolko et al., 2010) and from 1.0 to 1.56 in ventral striatum reactivity to reward (Epstein et al., 2006; Moses-Kolko et al., 2011; Moria J Smoski et al., 2009). Studies examining the association between amygdala activation and depressive symptom severity have yielded effect sizes (Cohen's d) ranging from 1.62 to 2.76 (Hamilton & Gotlib, 2008; Moses-Kolko et al., 2010).

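### Stated powers in sections 7.1 and 7.2 ignore the plan's own Bonferroni rule, and the 70% power given for hypothesis 2c belongs to r=.6, not r=.3

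*Combined protocol and SAP*

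**What the plan says.** Section 7.2, under Hypothesis testing, sets the error control: "For all hypothesis tests, we will use the Bonferroni method to correct for multiple comparisons". Neither the number of tests, nor their grouping, nor an adjusted alpha is given there or elsewhere. The same paragraph adds: "All hypothesis tests that are observed to be not statistically significant will be reported as being inconclusive".

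Section 7.2 then gives power for the lettered hypotheses, each time at alpha .05. For 1a, with f=0.3, it says "we will have 87% power to reject the null hypothesis with a total sample size of" 30. For 1b, 2a and 2b it states more than 99%, from f values of .5, .45 and .5. Hypothesis 1b also has its own imaging criterion: "Clusters will be thresholded at $Z>2.58$ or $p<.005$ corrected with a minimum contiguous cluster size of 8". The plan does not relate that criterion to Bonferroni.

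Section 7.1 justifies the sample size separately. It describes its method thus: "We approximated power and sample size using a simpler model comparing the two groups on change scores". It then states: "With 15 subjects per group, we have 80% power to detect effect sizes of 1.10". It gives neither alpha nor sidedness. The sample-size text in Appendix C repeats the claim without the 80%: "With 15 subjects per group, we have power to detect effect sizes of 1.10".

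For the secondary hypothesis 2c, section 7.2 cites a literature correlation of r=.6, then takes r=.3 with two-tailed .05 and n=15, and reports 70% power. For 1c, the same section takes a correlation of .3 with the same alpha, sidedness and n, and reports under 20%. It says that the study is not powered for either.

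**The concern.** Two statements for 1c and 2c have identical inputs and very different outputs, so at least one is wrong.

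The multiplicity rule and the power statements also fit together only on one reading. If Bonferroni applies across hypotheses, none of those tests is run at .05, and each power calculated at .05 is too high. If it applies only inside a hypothesis, for example across the regions in 2b, then .05 stands for 1a and 2a, but the plan does not say so. At stake are an honest statement of what 30 women can show, and whether the analyst knows before unblinding which alpha decides 1a, 2a and 2b.

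**Working it through.** **Hypothesis 2c.** Inputs from section 7.2: n=15, two-tailed .05, r=.3 (stated) or r=.6 (cited). With 13 degrees of freedom the critical t is 2.160, so the observed correlation must exceed 2.160/√(13+2.160²) = .514 in absolute value.

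- Simulation of bivariate-normal samples of 15 gives about 19% power at r=.3 and about 70% at r=.6.
- The Fisher z approximation agrees broadly. At r=.3, √12 × atanh(.3) = 1.07, and power is about Φ(1.07−1.96) = 19%. At r=.6, √12 × atanh(.6) = 2.40, and power is about 67%.
- A one-sided test at r=.3 reaches only about 30%. About 67 women would be needed for 70% power at r=.3.

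So 70% is the r=.6 figure, and the under-20% given for 1c is right.

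**Hypothesis 1a.** Inputs: f=.3, N=30, two groups, m=2 phases. For the group-by-phase interaction, λ = f²·N·m/(1−ρ) = .09×30×2/(1−ρ) = 5.4/(1−ρ), with 1 and 28 degrees of freedom. The between-phase correlation ρ is not stated. The plan's 87% at .05 is reproduced at λ=10.23, that is ρ about .47; ρ=.5 gives 88.7%.

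**Section 7.1.** For a two-sample test on change scores with 15 per group, λ = d²×15/2 = 1.10²×7.5 = 9.08, again with 1 and 28 degrees of freedom. At two-sided .05 this gives 82.8%, slightly better than the stated 80%.

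**Applying Bonferroni.** The family is not given, so a range is shown: two (the primary hypotheses of one aim), four (all primary hypotheses), six (all lettered hypotheses) and eight (four primary tests plus the four secondary correlations).

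| Family | alpha | 1a (ρ=.47) | 1a (ρ=.5) | Section 7.1, d=1.10 | d for 80% power |
|---|---|---|---|---|---|
| none | .05 | 87.0% | 88.7% | 82.8% | 1.06 |
| 2 | .025 | 79.1% | 81.5% | 73.7% | 1.18 |
| 4 | .0125 | 69.9% | 72.7% | 63.5% | 1.29 |
| 6 | .0083 | 64.1% | 67.1% | 57.4% | 1.36 |
| 8 | .00625 | 59.9% | 63.0% | 53.1% | 1.40 |

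The 1a figures depend on ρ. Over ρ from .3 to .7, power runs from 76.5% to 98.4% at .05 and from 55.0% to 93.4% at .0125.

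**Hypotheses 1b, 2a and 2b at their stated f, with ρ=.5 assumed.** For 2a, λ = .45²×60/.5 = 24.3, which gives 99.7% at .05 and 98.4% at .0125. For 1b and 2b, λ = .5²×60/.5 = 30, which gives over 99.9% and 99.6%. These figures treat each as a simple 2-by-2 interaction. For 1b that is a rough check, since cluster thresholding is a different procedure.

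**The case against.** The strongest reply is that the falls are conditional. The family is not in the documents, and a within-hypothesis reading leaves 1a's 87% untouched. Section 7.1 does not say its test is two-sided; one-sided, d=1.10 has 90.2% power at .05 and 73.7% at .0125. All of this stands, and it is why a range is given rather than one corrected figure. It does not remove the gap: the rule says all hypothesis tests, and nothing in the plan narrows it.

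The consequence is also limited. Section 7.1 has a separate argument for a small sample: if the effect is too small to be seen in it, "then this line of research, which involves significant participant burden, is not worth pursuing". Non-significant results are to be called inconclusive, and 2c has no part in the sample size.

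A reader might go further and infer that the powers above 99% are inflated, because section 7.2 cites d (1.3 for 1b, .95 for 2a, 1.58 to 1.96 for 2b) and then uses f without showing the conversion. The documents do not support that. If d is read on section 7.1's change-score scale, power at .05 is 93% (1b), 71% (2a) and 98.7% to 99.9% (2b). If instead f=d/2, the values are .65, .475 and .79 to .98, all above the f values used, so the plan's inputs would be conservative. The scale of d is not stated, so the direction is unknown. This is a reporting gap and not part of the point.

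A reader might also infer from the five-factor ANCOVA for 2b that its power has no defined target. The Study Summary describes a 2-by-2 design for each task and outcome, and Appendix C names the group-by-time interaction as the principal effect.

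**Conclusion.** Two things hold. First, the 70% for 2c is an error on its stated inputs: about 19% at r=.3, against 70% at r=.6. This needs no assumption beyond bivariate normality, and the plan's own 1c figure confirms it. It affects only a reported number.

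Second, the powers in 7.2, and in 7.1 if .05 was used there, are those of uncorrected tests if Bonferroni applies across hypotheses. With the four primary hypotheses as the family, 1a falls to about 70% and the section 7.1 effect of 1.10 to about 64%, both under the 80% that section 7.1 claims. These sizes rest on the assumed family, on ρ about .47 (back-solved from 87%) and on a two-sided test in 7.1. At their stated f, the powers of 1b, 2a and 2b change little.

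It would be tempting to conclude that the trial is too small, or that no primary test has a set threshold. Neither follows: the small-sample rationale does not rest on the corrected alpha, and 1b does have a stated threshold, whose relation to Bonferroni is what is missing.

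**What to change.** 1. In section 7.2, name the tests in the Bonferroni family and the adjusted alpha, for example the four primary hypotheses at .0125, or state that the correction applies only within a hypothesis. Say how it relates to the p<.005 cluster criterion for 1b.
2. If the correction is across hypotheses, restate 1a's power at the adjusted alpha, with the assumed correlation shown. Restate section 7.1 and the matching Appendix C text with alpha and sidedness. For a family of four that means about 70% for 1a, and for section 7.1 either about 64% at d=1.10 or 80% at d=1.29. For other families, use the table above.
3. Correct 2c to either r=.6 with 70% or r=.3 with about 19%.

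The cost is wording in sections 7.1 and 7.2 and in Appendix C. The downside is less favourable stated power. No change in N is needed.

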The objective of the current project is to extend this line of work by examining whether hormone sensitive women (HS+; n=15) show differences in the behavioral activation system relative to non-hormone sensitive women (HS-; n=15) under baseline and hormone challenge conditions using functional magnetic resonance imaging (fMRI) and behavioral tests. Our central hypothesis is that reproductive hormone changes are associated with dysregulated threat and reward processing and consequent irritability in HS+. The rationale for the proposed study is that employing a scaled down model of puerperal hormonal events permits the identification of a group of individuals homogeneous for hormone sensitivity (HS+), hence creating the best opportunity for disentangling the specific changes in brain function due to reproductive hormones (i.e., HS-) from those accompanying reproductive hormone-precipitated affective dysfunction (i.e., HS+). Because women will act as their own controls across time, this study design also allows for a powerful evaluation of state and trait variables that may contribute to irritability, including both threat processing and reward processing. Identifying both state and trait markers of irritability, and disentangling them from the effects of reproductive hormones on brain and behavior, will allow for the identification of neural substrates of irritability susceptibility that can be investigated across neuropsychiatric disorders. We plan to accomplish the objectives of this application by pursuing the following specific aims:

Aim 1: To determine the extent to which irritability is characterized by dysfunctional threat processing during reproductive hormone challenge relative to baseline in HS+ and HS-.

Hypothesis 1: We hypothesize that HS+ is characterized by behavioral activation in the context of potential threat. Given this hypothesis, we expect that:

Hypothesis 1a: Compared with HS-, HS+ will show a greater degree of threat attention bias as measured by the visual dot probe task during hormone addback relative to baseline.

Hypothesis 1b: Compared with HS-, HS+ will show reduced amygdala-medial PFC connectivity in response to threatening stimuli during hormone addback relative to baseline.

Hypothesis 1c (secondary): HS+ will show a significant association between self-reported irritability and 1) threat attention bias, and 2) amygdala-ventrolateral PFC connectivity during hormone addback.

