Null hypothesis 1c (secondary): In HS+, the degree of irritability, threat attention bias, and amygdala-medial PFC connectivity during hormone addback are unrelated in the target population.

Alternative hypothesis 1c (secondary): In HS+, irritability is associated with 1) threat attention bias, and 2) amygdala-medial PFC connectivity during hormone addback in the target population.

“Independent” variable: Irritability will be defined as scores on the IDAS-II ill temper scale at study visit 6.

“Dependent” variables: Threat attention bias at study visit 6 will be calculated in the same way as for hypothesis 1a. Amygdala-medial PFC connectivity at study visit 6 will be calculated in the same way as for hypothesis 1b.

Analysis: Pearson’s r will be calculated for correlations between irritability and 1) threat attention bias and 2) amygdala medial-PFC connectivity during hormone addback (study visit 6) in HS+.

Power: We have not powered to the study to assess secondary hypotheses. We used G*Power 3.1 for Mac to calculate power. Prior research suggests the association between irritability and threat attention bias has a medium effect size (Spearman’s $\rho=.3$) (Hommer et al., 2014). If we anticipate an effect size $\rho=.3$ and set $\alpha=.05$ (two-tailed), we will have less than 20% power to reject the null hypothesis with a HS+ sample size of $n=15$. There is not enough information to predict the strength of the association between irritability and amygdala medial-PFC connectivity.

Aim 2: To determine the extent to which irritability is characterized by dysfunctional reward processing during reproductive hormone challenge relative to baseline in HS+ and HS-.

Null hypothesis 2: HS+ is not characterized by increased frustration in the context of non-reward (i.e., when reward is expected) during hormone addback relative to baseline in the target population.

Alternative hypothesis 2: HS+ is characterized by increased frustration in the context of non-reward during hormone addback relative to baseline in the target population. Given this hypothesis, we will test the following sub-hypotheses:

Null hypothesis 2a: HS+ is not characterized by reactive aggression during hormone addback relative to baseline in the target population.

Alternative hypothesis 2a: HS+ is characterized by reactive aggression during hormone addback relative to baseline in the target population.

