Independent variables: Group (HS+ versus HS-) and Phase (Visit 3-baseline versus Visit 6-hormone addback)

Dependent variable: Reactive aggression will be defined as the number of point subtractions the participant makes during the Point Subtraction Aggression Paradigm.

Analysis: 2x2 Repeated Measures ANOVA will be used to analyze the effects of Group (HS- vs. HS+) and Phase (baseline vs. hormone addback) on threat attention bias.

Power: We used G*Power 3.1 for Mac to calculate power. We anticipate a large effect size based on a previous study examining reactive aggression using the Point Subtraction Aggression Paradigm in men who were treated with testosterone versus placebo ($d=.95$) . If we estimate the effect size $f=.45$ and set $\alpha=.05$, we will have greater than 99% power to reject the null hypothesis with a total sample size of N=30.

Null hypothesis 2b: HS+ is not characterized by reduced activation of the amygdala and ventral striatum in response to FNR during hormone addback relative to baseline in the target population.

Alternative hypothesis 2b: HS+ is characterized by reduced activation of the amygdala and ventral striatum in response to FNR during hormone addback relative to baseline in the target population.

Independent variables: Group (HS+ versus HS-) and Phase (Visit 3-baseline versus Visit 6-hormone addback)

Dependent variable: Activation in amygdala and ventral striatum (caudate, putamen, nucleus accumbens) ROIs during the Affective Posner Task. Event types include three categories: trial type (money, no money), validity (valid, invalid), and feedback (positive, negative, error). Combination of these three factors will be modeled using individual linear regression with a fixed-shape, gamma-variate response function, convolved with a boxcar function of the stimulus duration. FNR will be defined as the contrast between positive valid money trials and negative valid money trials (i.e., the difference between expecting money and getting it and expecting money and not getting it).

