Handedness Questionnaire	x							
Hormone History Questionnaire	x							
BIS/BAS	x		x			x		
Behavioral Tests								
Visual Dot Probe			x			x		
Point Subtraction Aggression			x			x		

Note: H/G = Hypogonadism; W/D = Withdrawal; F/U = Follow-up

b. Statistical analysis strategy:

This study has one between-subjects factor (group: HS+ versus HS-) crossed with one within-subjects factor (time: baseline versus hormone addback) with the outcome (percent signal changed) assessed in response to 2 tasks and in each of 2 ROIs. Thus, for a task/ROI combination, there is a 2-by-2 repeated measures design. We will analyze the data using linear mixed-effect models with an unstructured variance-covariance matrix. The principal effect of interest is the interaction, which will assess whether the groups differ with respect to the change from baseline to hormone addback in percent activation. We will also assess the difference between the groups at baseline and at addback. Hypotheses 1c and 2c will be addressed only in HS+, by correlating irritability with behavioral and neural responses to threat (1c) and FNR (2c). All hypothesis tests that are observed to be not statistically significant will be reported as being inconclusive.

2. The principal investigator will evaluate the progress of the trial, including periodic assessments of data quality and timeliness, participant recruitment, accrual and retention, participant risk versus benefit, performance of the trial site, and other factors that can affect study outcome.

B. Measures taken to insure data integrity and protection of databases

1. All study personnel are responsible for the collection and storage of data. All study staff participate in annual human subject training that includes education about responsibilities to minimize risk that confidentiality may be breached.
2. Participants will be identified by study ID number on all research documents and in electronic data files. All data will be stored in locked cabinets inside locked offices, and electronic data will be stored only on password-protected file servers only accessible from computers in the Psychiatry Department. Only study personnel will have access to these data. Qualtrics will be used to collect self-report questionnaire data for all participants with internet access. Participants will not enter any personally identifying information into the Qualtrics system, and they will be identified by their unique study ID only.

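### Section 7.2 words the four primary nulls (1a, 1b, 2a, 2b) as a change in HS+ alone, and for the behavioral endpoints 1a and 2a it never names the Group x Phase interaction as the deciding test

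*Combined protocol and SAP*

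**What the plan says.** **Section 2 (Study Objectives)** states all four primary hypotheses as comparisons with HS-. Hypothesis 1a begins "Compared with HS-, HS+ will show a greater degree of threat attention bias as measured by the visual dot probe task during hormone addback", taken relative to baseline. 1b, 2a and 2b have the same form. This is a difference in change.

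**Section 7.2** says that it details the null and alternative hypotheses to be tested, and leaves HS- out of each pair:
- 1a: "HS+ is not characterized by threat attention bias during hormone addback relative to baseline in the target population"
- 1b: "HS+ is not characterized by reduced amygdala-medial PFC connectivity in response to threatening stimuli during hormone addback relative to baseline in the target population"
- 2a: "HS+ is not characterized by reactive aggression during hormone addback relative to baseline in the target population"
- 2b: "HS+ is not characterized by reduced activation of the amygdala and ventral striatum in response to FNR during hormone addback relative to baseline"

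Under each pair it lists Group and Phase as independent variables. The analysis line for 1a is "2x2 Repeated Measures ANOVA will be used to analyze the effects of Group (HS- vs. HS+) and Phase" (baseline versus addback). The 2a line repeats it, and even names threat attention bias as its outcome. 1b has a 2x2 mixed-effects analysis of group and phase differences. 2b has a five-factor ANCOVA with no deciding term named.

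**Appendix C (Statistical analysis strategy)** says "The principal effect of interest is the interaction", in a paragraph whose outcome is percent signal change in the imaging tasks.

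**The concern.** Section 5.3 gives every woman the same drug protocol, so HS- is the only control for repeat testing, Lupron and the general effect of addback. The rationale in Sections 2 and 7.3 relies on this: HS- shows what the hormones do to brain function, and HS+ shows what accompanies the affective response.

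A null about HS+ alone is false whenever HS+ women change, even if HS- women change by the same amount. Neither of the two effects named in the 1a and 2a analysis lines tests the Section 2 hypothesis. Phase asks whether the average woman changes. Group asks whether the groups differ on average over both visits. Only Group x Phase asks whether they change differently. With a null that mentions only HS+ and a line that mentions only Group and Phase, a shared practice or drug effect could be reported as support for a primary hypothesis.

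**Working it through.** **1. The plan's own power figure for 1a.** Inputs from Section 7.2: f = 0.3, alpha = .05, N = 30, two groups, m = 2 visits, stated power 87%. The correlation between visits is not given, so rho = 0.5 is assumed.

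For a within-subject term, lambda = f² × N × m / (1 − rho) = 0.09 × 30 × 2 / 0.5 = 10.8, with 1 and 28 df. Power is 88.7%, within two points of the stated 87%. The range is 82.5% at rho = 0.4 and 94.4% at rho = 0.6.

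**2. Which test does that figure describe?** Same f and rho:

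| Test | lambda | df | Power |
|---|---|---|---|
| Group x Phase interaction | 10.8 | 1, 28 | 88.7% |
| Phase main effect | 10.8 | 1, 28 | 88.7% |
| Group main effect | 0.09 × 30 × 2 / 1.5 = 3.6 | 1, 28 | 44.9% |
| HS+ only, n = 15 | 0.09 × 15 × 2 / 0.5 = 5.4 | 1, 14 | 58.0% |

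The stated power fits a 30-woman test, not a test in HS+ alone. It cannot separate the interaction from the Phase main effect, because the two have identical power here. It therefore does not show which term decides 1a.

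**3. What a shared shift does.** Assume both groups change by delta, in SDs of the change score, with no group difference, and 15 women per group. The documents give no value for delta.

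- Phase main effect: noncentral t, df 28, noncentrality delta × √30. At delta = 0.5 this is 0.5 × 5.477 = 2.739.
- Group x Phase: a two-sample comparison of change scores. Its noncentrality is 0 whatever delta is.

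| Shared shift (SD) | Phase, alpha .05 | Phase, alpha .0125 | Interaction |
|---|---|---|---|
| 0.3 | 35% | 17% | nominal |
| 0.5 | 75% | 54% | nominal |
| 0.8 | 99% | 95% | nominal |

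The .0125 column takes the Section 7.2 Bonferroni rule over four primary tests (.05 / 4). The plan does not state the family size, so that too is an assumption. A 50,000-run simulation at alpha .05 put the interaction's rejection rate between 4.7% and 5.1% for shifts of 0 to 0.8.

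**4. What the rest of the plan points to.**
- Section 7.1 bases power on comparing the two groups on change scores, and names threat attention bias and reactive aggression among them. In a 2x2 design that comparison is the Group x Phase interaction.
- Section 3.2 (Aim 1) and the Appendix C overview (both aims) define the primary endpoints in HS+ compared with HS-, during challenge relative to baseline.
- The Study Summary crosses group with time for each outcome, behavioral ones included.
- Appendix C makes the interaction principal for percent activation. That covers 2b and arguably 1b, since connectivity is not literally percent activation. It does not cover the behavioral outcomes.

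Only the null and alternative sentences in Section 7.2, and the unnamed term in the 1a and 2a analysis lines, depart from this.

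**The case against.** The strongest reply is that the intent is clear and the models are right. Group is a factor in every primary analysis. All four power statements use N = 30. Where the plan means HS+ alone, as in 1c and 2c, it says so and uses n = 15. On that view the null sentences are loose shorthand, and Sections 3.2 and 7.1 supply the comparison. Most of this stands: the intended contrast is very probably the interaction, and the planned models contain it.

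It does not remove the point. Section 7.2 is where the tests are specified. Its sentences state a different hypothesis, and for 1a and 2a no passage names the interaction as the deciding term.

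Three stronger readings are tempting and are not supported:

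- *The plan will test HS+ on its own.* Such a test would reject 19%, 44% and 82% of the time for shared shifts of 0.3, 0.5 and 0.8 SD at alpha .05. With a true d of 1.10 split evenly between the groups in opposite directions, it would have 51% power against 83% for the interaction. These figures describe a literal reading of the null sentences, since no HS+-only test is planned for a primary hypothesis.
- *False positives rise to about 14%.* That requires counting any one of the three ANOVA terms as support. No passage says so, and it ignores the Bonferroni rule.
- *All four endpoints are equally exposed.* Appendix C largely settles 2b and arguably 1b.

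**Conclusion.** The inconsistency is real in the wording of all four primary pairs, and has practical consequence mainly for 1a and 2a. As written, a Phase effect shared by both groups could be taken as rejecting the stated null for those endpoints, although it says nothing about hormone sensitivity.

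The 75% and 54% rates at a 0.5 SD shared shift illustrate the exposure and do not predict it. They depend on an assumed shift and, for the second, an assumed Bonferroni family of four. The conclusion itself rests on the text and not on those figures.

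Severity is moderate. A reader might infer that the primary analysis is invalid or the study wrongly sized for this reason. The documents do not support that: the planned models can test the Section 2 hypotheses, and naming the interaction leaves the 1a power at 88.7% (rho = 0.5), close to the stated 87%.

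**What to change.** In Section 7.2:

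1. Restate the four primary pairs. Null: the mean change from Visit 3 to Visit 6 does not differ between HS+ and HS-. Alternative: it differs. Apply this to threat attention bias, amygdala-medial PFC connectivity, reactive aggression, and amygdala and ventral striatum activation.
2. Name Group x Phase as the single confirmatory term for each hypothesis, explicitly in the 1a and 2a analysis lines. For 2b, say how that contrast is taken from the five-factor ANCOVA.
3. Report Group, Phase and within-group changes as descriptive only.
4. While editing the 2a line, correct its outcome to reactive aggression.

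This agrees with Section 2, Section 3.2, the change-score basis in Section 7.1 and the Appendix C sentence. It costs a wording amendment, best made before analysis, with no new data, participants or change in sample size.
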